2.1 Primary Efficacy Measures

The primary efficacy measures are the following, listed in hierarchical order:

Absence of anterior chamber cells (i.e., score of "0") at Visit 6 (
Absence of pain (i.e., score of "0") at Visit 4

2.3 Safety Measures

[figure not shown]
The primary safety measures include the following:

[figure not shown]
- Change from baseline in pin-hole visual acuity (VA) (without any other correction) as measured on the ETDRS chart
- Change from baseline of intraocular pressure (IOP)
- Change in endothelial cell density assessed at Visit 8

• Adverse event (AE) rates

Additional safety measures described in the protocol include:

- Slit lamp biomicroscopy parameters;
- Dilated indirect ophthalmoscopy parameters;
- Endothelial cell parameters, including density, %hexagonal, and %CV.

3. Study Design and Procedures

3.1 General Study Design

This is a multi-center, randomized, double-masked, placebo (vehicle)-controlled study, designed to evaluate the efficacy and safety of OCS-01 compared to placebo (vehicle) in treating inflammation and pain following cataract surgery.

Subjects will be randomized 1:1 to receive OCS-01 or placebo (vehicle) QD. Subjects will dose 1 drop in the study eye QD for 14 days, beginning 1 day post-surgery in the operated eye. The study will last 91-125 days, including screening and a follow-up visit at Visit 8 (Day 90) for endothelial cell density assessment.

Study visits will be followed by the expected study day corresponding to the visit in parentheses in all tables and listings to enable reviewers to understand the assessment timing without referring to the protocol visit schedule. Table 1 shows the scheduled study visits, their planned study day, and the acceptable visit window for each study visit:

Table 1. Study Visit Windows

Scheduled Visit	Planned Study Day	Visit Window
Visit 1	Screening/Baseline Evaluations	-28 to -1 days prior to surgery
Visit 2	Day 1	18 to 30 hours post-surgery
Visit 3	Day 2	± 0 days
Visit 4	Day 4	± 1 day
Visit 5	Day 8	± 1 day
Visit 6	Day 15	± 2 days

Scheduled Visit	Planned Study Day	Visit Window
Visit 7	Day 22	± 2 days
Visit 8	Day 90	± 7 days

3.2 Schedule of Visits and Assessments

The schedule of visits and assessments is provided in Table 2.

Table 2. Schedule of Visits and Assessments

	Visit 1	Visit 2	Treatment Period			Follow-up		
Study Parameter	(-28 to -1 Day(s) Prior to Surgery)	(Day 1, 18-30hrs Post- Surgery)	Visit 3 (Day 2, telephone call)	Visit 4 (Day 4 ± 1)	Visit 5 (Day 8 ± 1)	Visit 6 (Day 15 ± 2)	Visit 7 (Day 22 ± 2)	Visit 8 (Day 90 + 7)
Informed Consent / HIPAA	X							
Demographic Data	X							
Medical and Medication History	X							
Urine pregnancy Test	X						X	
Review Inclusion / ExclusionCriteria	х	Х						
Medical and Medications Update		Х		Х	Х	Х	Х	
Ocular Pain (Study Eye Only)	Х	Х	Х	Х	Х	Х	Х	
Pin-hole Visual Acuity	X	X		X	Х	Х	Х	
Slit lamp Biomicroscopy	X	Х		Х	Х	Х	Х	
Ocular Inflammation Assessment ofthe Anterior Chamber Cell and Flare(Study Eye Only)	Х	Х		Х	х	х	х	
Intraocular Pressure	X			X	X	X	X	
Randomization		Х						
Dilated Indirect Ophthalmoscopy	X						X	
Dispense Study Medication andDosing Diary		Х						
AE Query		X		X	Х	X	X	Х
Endothelial Cell Density	Х							X
Exit from Study								Х

AE = Adverse Event; HIPAA = Health Insurance Portability and Accountability Act
Study eye only: Ocular Inflammation Assessment of the Anterior Chamber Cell and Flare; Ocular Pain

4. Study Treatments

Study eyes will be treated with either OCS-01 (dexamethasone Ophthalmic Suspension, 1.5% (15 mg/mL) QD or placebo (vehicle) QD ophthalmic suspension during the treatment period of the study.

4.1 Method of Assigning Subjects to Treatment Groups

At Visit 2 each subject who signed an informed consent form at Visit 1 will be assigned a screening number. Screening numbers will be assigned in sequential order at each site beginning with 001 and will follow the two-digit site number (e.g., subject 077 at Site 99 will have Screening Number 99-077). No subjects should be rescreened except in special circumstances in which sites should obtain approval to re-screen. Inclusion and exclusion criteria will be reviewed, and qualifying subjects will be enrolled into the study. Each subject who qualifies for entry will be assigned a randomization number and corresponding treatment according to the randomization code. Subjects will be randomly assigned to either OCS-01 QD or placebo (vehicle) QD using a 1:1 assignment ratio, stratified by site, via an interactive response system.

[figure not shown]
Randomization numbers will be assigned in sequential order at each site beginning with 1001 and will follow the two digit site number (e.g., randomized subject 1005 at Site 99 will have Randomization Number 99-1005). Sequentially numbered study drug kits will be provided to each investigational site, in accordance with the site-specific randomized study drug kit list, which consists of sequential 4-digit kit ID numbers. The interactive response system (IRT) will be utilized to assign the randomized subject the lowest 4-digit study drug kit number available at their investigative site associated with randomized treatment, in a masked manner to the site study team. If a randomized subject is discontinued from the study for any reason, their randomization number and randomized study drug kit number will not be reassigned.

The subject number will be used to identify subjects in all datasets and listings for this study.

4.2 Masking and Unmasking

An independent, unmasked biostatistician who is not otherwise involved in the trial will generate the complete randomized study drug kit list. The subject, Sponsor, Investigators, and study staff will be masked during the randomization process and throughout the study.

The randomization code should be broken only in the event of a medical emergency, or when knowing the treatment assignment is absolutely necessary for the medical management of the study subject. When possible (i.e., in non-emergency situations), the study Sponsor or representative should be notified prior to unmasking study drug. In emergency situations, the Investigator must notify the Sponsor within 24 hours after determining that it is necessary to unmask the treatment assignment. The Investigator must also indicate in source documents and in the eCRF that the mask was broken and provide the date, time, and reason for breaking the mask. Any AE or SAE associated with breaking the mask must be recorded and reported as specified in the protocol. More details about the emergency unmasking process can be found in the IRT Plan as a separate document.

6. Data Preparation

6.1 Input Data

Study data from source documents will be entered into the electronic Case Report Forms (eCRF) supplied by Statistics & Data Corporation (SDC) using the electronic data capture (EDC) system iMedNet™ v1.221.2 or higher. Additional details about the EDC system can be found in the Data Management Plan as a separate document.

In addition, the following study data which is not captured directly within the iMedNet system but is obtained from external vendors will also be included for analysis. These data sources are described in detail in data transfer agreements developed between data management and the respective external laboratory or reading center:

Endothelial cell density

After data are entered into the clinical study database, electronic edit checks and data review will be performed. All data validation specifications and procedures are detailed in the Data Validation Manual as a separate document. When the database has been declared to be complete and accurate and all prerequisites for database lock have been met, including availability of all external data, the database will be locked. Following database lock, approval will be obtained from the Sponsor to unmask the study.

Final analysis will be carried out after the following have occurred:

- Database lock has occurred, including receipt of all final versions of external vendor data, with written authorization provided by appropriate SDC and Sponsor personnel.
- Protocol deviations have been classified (major/minor deviations).
- Analysis populations have been determined.
- Randomized treatment codes have been unmasked.

Any changes to the database after data have been locked or after unmasking can only be made with the approval of the Sponsor in consultation with SDC and per SDC standard operating procedures (SOPs). Adjustments to or repeats of analyses will be conducted as appropriate and in consultation with Sponsor.

6.2 Output Data

Data from iMedNet and external data will be transferred to Biostatistics and incorporated into standard formats following the Study Data Tabulation Model (SDTM). Data will then be mapped to analysis datasets using the Analysis Data Model (ADaM). Both SDTM and ADaM-formatted data will be used to create the subject listings, while all tables and figures will be based on the ADaM-formatted data.

SDTM will follow the SDTM version 1.7 model and will be implemented using the SDTM Implementation Guide version 3.3 and the most recent version of SDTM Controlled Terminology at the time of programming start. ADaM data will follow the ADaM version 2.1 model and will be implemented using the ADaM Implementation Guide version 1.1. Both SDTM and ADaM will be validated using Pinnacle 21 version 4.02. Any discrepancies in the validation will be noted in reviewer's guides accompanying the final data transfers.

Define.xml will be created for SDTM and ADaM using the Define-XML version 2.0 model.

7. Analysis Populations

7.1 Full Analysis Set

The full analysis set (FAS) will consist of all randomized subjects, analyzing subjects under the treatment to which they were randomized.

7.2 Per Protocol

The per protocol (PP) population is a subset of the FAS and includes subjects who remain in the study through Visit 6 () with no major protocol violations that would affect the assessment of the primary efficacy endpoints of the study, analyzing subjects under the treatment received. Major protocol violations will be identified prior to unmasking treatment.

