Sections 13.1.1 to 13.1.5 describe the sensitivity analyses for the handling of intercurrent events to be performed for the primary efficacy variables.

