13.1.3 SENSITIVITY ANALYSIS III

The primary efficacy analysis will be performed using the PP population with observed data only. Treatment comparisons will be made using Pearson's chi-squared test. If any of the expected cell counts are less than five, an exact 95% CI for the difference in proportions and Fisher's exact test will be used instead.

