13.1.4 SENSITIVITY ANALYSIS IV

The primary efficacy analysis will be performed using the FAS with observed data only. Treatment comparisons will be made using Pearson's chi-squared test. If any of the expected cell counts are less than five, an exact 95% CI for the difference in proportions and Fisher's exact test will be used instead.

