14.7 Clinical Laboratory Data

15. Interim Analyses

Interim analyses will not be performed for this study.

16. Changes from Protocol-Stated Analyses

The SAP includes the following changes from the protocol-stated analyses:

 After discussion with the sponsor, the definition of the Per Protocol population in the SAP has omitted the parenthetical "(or who discontinue due to adverse event or lack of efficacy or receive rescue medication prior to Visit 6 [Day 15])" which is present in the Per Protocol population definition from the protocol version 1.0.

17. References

- ICH Harmonised Tripartite Guideline: Statistical Principles for Clinical Trials E9. International Council for Harmonisation of Technical Requirements for Pharmaceuticals for Human Use. 05 February 1998.
- ICH Harmonised Tripartite Guideline: Addendum on Estimands and Sensitivity Analysis in Clinical Trials to the Guideline on Statistical Principles for Clinical Trials E9(R1). International Council for Harmonisation of Technical Requirements for Pharmaceuticals for Human Use. 20 November 2019.
- ICH Harmonised Tripartite Guideline: Structure and Content of Clinical Study Reports E3.
 International Council for Harmonisation of Technical Requirements for Pharmaceuticals for Human Use. 30 November 1995.

18. Revision History

Documentation of revision to the SAP will commence after approval of the final version 1.0.

19. Tables

Tables that will be included in the topline delivery are shown in boldface font.

Table Number	Title	Population
Table 14.1.1.1	Subject Disposition	
Table 14.1.1.2	Reasons for Screen Failures	Screen Failed Subjects
Table 14.1.2	Demographics	Full Analysis Set
Table 14.1.3.1	Ocular Medical History	Safety Population
Table 14.1.3.2	Non-Ocular Medical History	Safety Population
Table 14.1.4.1	Ocular Concomitant Medications	Full Analysis Set
Table 14.1.4.2	Non-Ocular Concomitant Medications	Full Analysis Set
Table 14.1.4.3	Post-Baseline IOP-Lowering Medications by Visit	Safety Population
Table 14.2.1.1.1	Absence of Anterior Chamber Cells at Visit 6 (Day 15) in Study Eyes - Primary Analysis	Full Analysis Set
Table 14.2.1.1.2	Absence of Anterior Chamber Cells at Visit 6 (Day 15) - Sensitivity Analysis I	Full Analysis Set
Table 14.2.1.1.3	Absence of Anterior Chamber Cells at Visit 6 (Day 15) - Sensitivity Analysis II	Full Analysis Set

Table 14.2.1.1.4	Absence of Anterior Chamber Cells at Visit 6 (Day 15) - Sensitivity Analysis III	Per Protocol Population

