Table 14.2.1.1.5	Absence of Anterior Chamber Cells at Visit 6 (Day 15) - Sensitivity Analysis IV	Full Analysis Set
Table 14.2.1.1.6	Absence of Anterior Chamber Cells at Visit 6 (Day 15) - Sensitivity Analysis V	Full Analysis Set
Table 14.2.1.2.1	Absence of Ocular Pain at Visit 4 (Day 4) - Primary Analysis	Full Analysis Set
Table 14.2.1.2.2	Absence of Ocular Pain at Visit 4 (Day 4) - Sensitivity Analysis I	Full Analysis Set
Table 14.2.1.2.3	Absence of Ocular Pain at Visit 4 (Day 4) - Sensitivity Analysis II	Full Analysis Set
Table 14.2.1.2.4	Absence of Ocular Pain at Visit 4 (Day 4) - Sensitivity Analysis III	Per Protocol Population
Table 14.2.1.2.5	Absence of Ocular Pain at Visit 4 (Day 4) - Sensitivity Analysis IV	Full Analysis Set
Table 14.2.1.2.6	Absence of Ocular Pain at Visit 4 (Day 4) - Sensitivity Analysis V	Full Analysis Set
20		
A		
2)		100
Table 14.3.1.1	Overall Summary of Treatment-Emergent Adverse Events	Safety Population
Table 14.3.1.2.1	Ocular Treatment-Emergent Adverse Events by System Organ Class and Preferred Term	Safety Population
Table 14.3.1.2.2	Non-Ocular TEAEs by System Organ Class and Preferred Term	Safety Population
Table 14.3.1.3.1	Ocular TE-SAEs by System Organ Class and Preferred Term	Safety Population

Table 14.3.1.3.2	Non-Ocular TE-SAEs by System Organ Class and Preferred Term	Safety Population
Table 14.3.1.4.1	Suspected Treatment-Related Ocular TEAEs by System Organ Class and Preferred Term	Safety Population
Table 14.3.1.4.2	Suspected Treatment-Related Non-Ocular TEAEs by System Organ Class and Preferred Term	Safety Population
Table 14.3.1.5.1	Expected Ocular TEAEs by System Organ Class and Preferred Term	Safety Population
Table 14.3.1.5.2	Expected Non-Ocular TEAEs by System Organ Class and Preferred Term	Safety Population
Table 14.3.1.6.1	Unexpected Ocular TEAEs by System Organ Class and Preferred Term	Safety Population
Table 14.3.1.6.2	Unexpected Non-Ocular TEAEs by System Organ Class and Preferred Term	Safety Population
Table 14.3.1.7.1	Ocular TEAEs by System Organ Class, Preferred Term, and Maximum Severity	Safety Population
Table 14.3.1.7.2	Non-Ocular TEAEs by System Organ Class, Preferred Term and Maximum Severity	Safety Population
Table 14.3.2	Pin-Hole Visual Acuity (logMAR) in Study Eyes by Visit	Safety Population
Table 14.3.3	Intraocular Pressure in Study Eyes by Visit	Safety Population
Table 14.3.4	Endothelial Cell Density in Study Eyes by Visit	Safety Population

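### The single per-protocol set requires staying in the study to Visit 6 (Day 15), so Sensitivity Analysis III of Day 4 pain drops valid scores from subjects who leave between Visits 4 and 6

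*SAP*

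**What the plan says.** SAP 7.2 gives one PP population, a "subset of the FAS and includes subjects who remain in the study through Visit 6", with no major violation affecting the assessment of the primary endpoints. No version specific to an endpoint appears. SAP Tables 1 and 2 place Visit 4 at Day 4 ± 1 and Visit 6 at Day 15 ± 2.

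SAP 13.1 names two primary variables: absence of anterior chamber cells at Visit 6 and absence of pain at Visit 4. It then states: "Sections 13.1.1 to 13.1.5 describe the sensitivity analyses for the handling of intercurrent events to be performed for the primary efficacy variables". For Analysis III, SAP 13.1.3 says: "The primary efficacy analysis will be performed using the PP population with observed data only". The table list in SAP 19 contains "Absence of Ocular Pain at Visit 4 (Day 4) - Sensitivity Analysis III" as Table 14.2.1.2.4, with the PP population. The FAS counterpart is Table 14.2.1.2.5, "Absence of Ocular Pain at Visit 4 (Day 4) - Sensitivity Analysis IV", for which SAP 13.1.4 says: "The primary efficacy analysis will be performed using the FAS with observed data only".

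The PP definition in Protocol 11.3 also ran to Visit 6, but it kept subjects who discontinued for an adverse event or lack of efficacy, or who were rescued, before that visit. SAP 16 declares the change: "After discussion with the sponsor, the definition of the Per Protocol population in the SAP has omitted the parenthetical" that held this exception. It gives no reason beyond the discussion and does not mention Day 4 pain.

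Under Protocol 6.6 and 9.6.2, subjects who stop study drug or are rescued stay enrolled and continue their visits.

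**The concern.** For the cell endpoint, a Visit 6 retention rule costs nothing in an observed-data analysis, since a subject who has left has no Visit 6 value. For pain, the value was recorded at about Day 4, and leaving the study later does not make it less complete or less compliant. Membership of the Day 4 analysis set then depends on something that happens after Day 4 and may be related to treatment or to pain itself. Adverse events and lack of efficacy are among the discontinuation reasons in SAP 9, and SAP 16 now excludes those leavers too.

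At stake is how Analysis III can be read. If its Day 4 pain result differs from that of Analysis IV, the reader cannot tell whether protocol violations or later exits caused the difference.

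**Working it through.** **Who is affected.** The documents state no figure to reproduce, so the first step is to set the rules side by side.

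- Pain endpoint: Visit 4, Day 3 to 5 with its window.
- Retention visit for PP: Visit 6, Day 13 to 17 with its window.
- Gap: 15 − 4 = 11 planned days; with windows, 13 − 5 = 8 to 17 − 3 = 14 days.
- A subject who leaves the study in this gap has an observed Day 4 score but fails SAP 7.2.
- A subject who stops drug or is rescued but stays enrolled still meets the retention condition.
- A subject who leaves after Visit 6 is unaffected.

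**What the change in SAP 16 does.** Under the protocol, gap leavers for other reasons (for example loss to follow-up or withdrawn consent) were already dropped. Under the SAP, adverse-event and lack-of-efficacy leavers are dropped as well.

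**Which other pain analyses keep the scores.**

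- Analysis IV keeps all observed Day 4 scores.
- Analyses I, II and V set post-rescue data to failure (SAP 13.1.1, 13.1.2, 13.1.5), so they keep the observed score only for leavers not rescued before Visit 4.
- The primary analysis follows SAP 2.5 (cross-referenced in SAP 8.2), which is not visible in the public text.

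**Size, under assumed rates.** From the documents: 120 per arm and two-sided 0.05. Assumed: true pain-free rates *p* of 65% (OCS-01) and 50% (vehicle); share *l* leaving between Visits 4 and 6; pain-free rate *q* = 20% among leavers. After leavers are removed:

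rate = (p − l·q)/(1 − l), n = 120·(1 − l)

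Example, exits 1% against 3%:

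- OCS-01: (0.65 − 0.01 × 0.20)/0.99 = 65.45%
- Vehicle: (0.50 − 0.03 × 0.20)/0.97 = 50.93%
- Difference: 14.5 points

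| Exits, OCS-01 vs vehicle | PP rates (%) | Difference (points) |
|---|---|---|
| none | 65.0 vs 50.0 | 15.0 |
| 1% vs 3% | 65.5 vs 50.9 | 14.5 |
| 2% vs 5% | 65.9 vs 51.6 | 14.3 |
| 3% vs 1% | 66.4 vs 50.3 | 16.1 |
| 5% vs 2% | 67.4 vs 50.6 | 16.8 |
| 3% each | 66.4 vs 50.9 | 15.5 |
| 5% each | 67.4 vs 51.6 | 15.8 |

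The most unequal pairs within 1% to 5% go slightly further: 1% vs 5% gives 65.45 − 51.58 = 13.9 points, and 5% vs 1% gives 67.37 − 50.30 = 17.1.

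Power from the pooled two-proportion z test is 65% with no exits. It is 62% and 60% in the two rows with more exits on vehicle, and 71% and 74% in the two rows with more exits on OCS-01.

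If leavers are pain-free as often as the rest of their arm (*q* = *p*), then (p − l·p)/(1 − l) = p. The difference stays at 15.0 points and only the sample shrinks. If the set requires presence only through Visit 4, later exits cause no shift in any row.

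**The case against.** The strongest reply is that this is a design preference. A single PP set describing subjects who stayed through the 14-day treatment period is coherent and contains no contradiction. The change to it was declared in SAP 16. Analysis IV already shows the Day 4 pain result with every observed score. This stands as a limit on importance. It does not remove the selection, because comparing Analyses III and IV shows all PP exclusions together and cannot separate later exits from violations.

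A reader might infer from Protocol 11.6.2, which runs the primary analyses secondarily on the PP population, that Analysis III carries formal weight. SAP 1 says that its methods supersede the protocol's, and in the visible SAP the PP efficacy analysis is one of five sensitivity analyses.

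A reader might also infer that the primary analysis and Analyses I, II and V certainly preserve these scores. That is too firm. Post-rescue data become failures in I, II and V, SAP 2.5 cannot be read, and Protocol 6.6 says that rescued or off-drug subjects are not analysed for primary endpoint efficacy.

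Finally, the size rests wholly on assumed rates, and the assumption that leavers are less often pain-free produces all of the shift. That is correct. Power also means little for an analysis without a decision rule.

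**Conclusion.** The point holds as a minor one. The retention rule suits the Visit 6 cell endpoint but not Day 4 pain, and Analysis III for pain discards complete data because of a later event. Nothing in the visible SAP corrects this within that analysis.

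The documents cannot give its size. For the assumed rates and the six exit pairs tabled, the shift runs from about −0.7 to +1.8 points on a difference of 15.0, in either direction. It is zero if nobody leaves in the gap or if leavers resemble their arm. The documents do not support a claim that the trial's conclusion is at risk: no visible success rule depends on Analysis III, and Analysis IV retains all observed Day 4 scores.

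**What to change.** In SAP 7.2, set the retention visit by endpoint: through Visit 4 for absence of pain, and through Visit 6 for absence of anterior chamber cells. Leave the major-violation criterion as it is, since no problem has been shown with it. Use the first set for Table 14.2.1.2.4 and the second for Table 14.2.1.1.4. Show both flags in the SAP 9 disposition summary and in Listing 16.2.3. Analysis III remains an observed-data analysis.

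This takes one amended definition and one extra flag before unmasking, with no new data. Protocol 11.3 allows populations to be refined in the SAP at that stage. The downside is two PP flags and two denominators to report instead of one.
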